10.14 APPENDIX 14: DEFINITION OF LINE OF THERAPY

One line of therapeutic regimen is defined as a composite of one or several treatment modalities (may include transplantation, radiotherapy and/or drug[s]) instituted based on the results of a restaging exam.

If a regimen is composed of several drugs and one of the drugs is stopped for any reason, the regimen must be considered as ongoing until the entire regimen is stopped due to any reason.

If a new line of therapy is instituted based on the results of a restaging exam, it is usually considered a distinct line of therapy (38).

10.15 APPENDIX 15: ABBREVIATIONS

ADA:	anti-drug antibody
ADL:	activities of daily living
AE:	adverse event
AESI:	adverse event of special interest
ALT:	alanine aminotransferase
aPTT:	activated Partial Thromboplastin Time
AST:	aspartate aminotransferase
ASTCT:	American Society for Transplantation and Cellular Therapy
CBR:	clinical benefit rate
cHL:	classic Hodgkin lymphoma
CI:	confidence interval
CLS:	capillary leak syndrome

COVID-19:	Corona Virus Disease 2019
CR:	complete response
CRS:	cytokine release syndrome
DLBCL:	diffuse large B cell lymphoma
DLT:	dose-limiting toxicity
DMC:	Data Monitoring Committee
DoR:	duration of response
ECOG:	Eastern Cooperative Oncology Group
eGFR:	estimated glomerular filtration rate
EOT:	end of treatment
IB:	Investigator's brochure
ICANS:	immune cell-associated neurotoxicity syndrome
ICF:	informed consent form
IHC:	immunohistochemistry
IL-2:	interleukin 2
IMP:	investigational medicinal product
INR:	International Normalized Ratio
irAE:	immune-related adverse event
IRR:	infusion-related reaction
IV:	intravenous
MCP-1:	monocyte chemoattractant protein-1
MTD:	maximum tolerated dose
NCI-CTCAE:	National Cancer Institute Common Terminology Criteria for Adverse Events
NHP:	non-human primate
NIMP:	non-investigational medicinal product
NK:	natural killer
NSCLC:	non-small cell lung cancer
PD:	progressive disease
PD-L1:	programmed death-ligand 1
PFS:	progression free survival
PK:	pharmacokinetic
PMBCL:	primary mediastinal large B cell lymphoma
PO:	oral route
PR:	partial response
pRBC:	packed red blood cell
Q2W:	every 2 weeks
Q3W:	every 3 weeks
RCC:	renal cell carcinoma
RP2D:	recommended Phase 2 dose
SAE:	serious adverse event
SARS-CoV-2:	severe acute respiratory syndrome coronavirus 2
SB:	Study Board
SUSAR:	suspected unexpected serious adverse reaction
TLS:	tumor lysis syndrome
TRAE:	treatment-related adverse event
TRR:	time to response

ULN: upper limit of normal
VLS: vascular leak syndrome
WOCBP: woman of childbearing potential

10.16 APPENDIX 16: PROTOCOL AMENDMENT HISTORY

The Protocol Amendment Summary of Changes Table for the current amendment is located directly before the Table of Contents (TOC).

1.2 Schema	The Graphical study design for Cohort A has been updated with the instruction for FDG-PET.	For clarity and consistency.
1.3 Schedule of activities (SOA)	The assessment of troponin level has been added. For footnote "d", the following sentence "Information on the first subsequent anticancer treatment, best reported response, and date of progression will also be collected." has been deleted.	To allow assessment of any potential cardiotoxicity. Reduction in protocol complexity and patient/site burden.

Section # and Name	Description of Change	Brief Rationale
	Footnote "e" has been newly added for clarification on C1D2, D3 visits. The subsequent footnotes are re-numbered accordingly.	For clarity.
	Footnote "f" for blood draws and/or tumor biopsy for biomarker assessment has been removed and changed to "Study Board may decide to cancel safety assessment on C1D15, upon agreement with Sponsor, if safety data justifies it." The reference to the footnote "f" has been deleted at C1D8 in the SOA.	To make operational procedures easier.
	For footnote "i" (previous footnote h), tumor lysis laboratory tests on C1D1 have been changed from "for all participants" to "for safety run-in participants or participants who are hospitalized".	For clarity.
1.3 Schedule of Activities (SOA), 10.7 Appendix 7: Country-Specific Requirements	Requirement of human immunodeficiency virus (HIV) has been added at screening for participants in France and specified in SOA newly added footnote "m" and country-specific requirements sections.	Regulatory Authority (ANSM) request.

1 PROTOCOL SUMMARY

Please refer to the Master Protocol for description of common protocol elements. Substudy specific protocol elements are described below.

1.1 SYNOPSIS

Protocol title:

A Phase 2 non-randomized, open-label, multi-cohort, multi-center study assessing the clinical benefit of SAR444245 (THOR-707) combined with pembrolizumab for the treatment of adults and adolescents with relapsed or refractory classic Hodgkin lymphoma

Brief title: A study of SAR444245 combined with pembrolizumab for the treatment of adults and adolescents with cHL

Rationale:

Preclinical studies demonstrated that treatment with SAR444245 leads to polyclonal expansion of CD8+ T cells in murine and non-human primate (NHP) models while anti programmed cell death-1 (anti-PD1) antibody prevents T cell suppression through the programmed cell death-1/programmed cell death-ligand 1 (PD1/PD-L1) pathway. The combination of anti-PD1 treatment with SAR444245 was tested in the syngeneic murine colon cancer CT-26 model and induced enhanced anti-tumor activity as demonstrated by an increased number of complete responses (CR) and tumor-free surviving animals compared to each agent in monotherapy. These data support evaluation of SAR444245 in combination with an anti-PD1 antibody.

The proposed study aims to establish proof-of-concept that non-alpha interleukin 2 (IL-2) SAR444245 combined with the anti-PD1 antibody, pembrolizumab in trial participants with classic Hodgkin lymphoma (cHL) who are anti-PD-(L)1-naïve and have received at least 2 or 3 lines of systemic therapy .

Objectives and endpoints

Please refer to the master protocol for description of common objectives and endpoints. Substudy-specific objectives and endpoints are summarized below.

Objectives	Endpoints
Primary	
 To determine the antitumor activity of SAR444245 with or without other anticancer therapies.
Secondary	
 Complete response rate (CRR) defined as the proportion of participants who have a complete response (CR) determined by Investigator per Lugano response criteria 2014 (1). Objective response rate (ORR) defined as the proportion of participants who have CR or partial response (PR) determined by Investigator per Lugano response criteria 2014 (1).

[figure not shown]
Overall design:

Please refer to the master protocol.

Brief summary:

Cohort A: This substudy will include approximately 25 participants with cHL who have received at least 2 or 3 lines of systemic therapy and will assess SAR444245 combined with pembrolizumab as at least 3rd or 4th line of therapy.

A graphical presentation of the substudy schema is shown in [Figure 1](#).

Figure 1 - Overall study schema

a The DLT observation period is 21 days for Cohort A.

b Including participants enrolled in the safety run-in at the confirmed safe dose.

Abbreviations: 3L/4L: third-line or fourth-line; auto-SCT: autologous stem-cell transplantation; cHL: classic Hodgkin lymphoma; DLT: dose limiting toxicity; N: number; PD1: programmed cell death 1.

Number of participants:

Overall, approximately 25 participants will be treated in Cohort A

Intervention groups and duration:

Please refer to the master protocol for common description of the study duration. For Cohort A, the maximum cycles allowed are 35 cycles.

Study interventions**Cohort A: cHL participants, SAR444245 + pembrolizumab as at least 3L/4L therapy*****Dosing sequence:***

[REDACTED]

Investigational medicinal product(s)***Pembrolizumab***

- Formulation: Keytruda® (pembrolizumab) as 100 mg/4 mL (25 mg/mL) solution in single-dose vials.
- Route of administration: intravenous (IV) infusion.
- Dose regimen: Pembrolizumab will be administered at a dose of 200 mg (for pediatric participants: 2 mg/kg, up to maximum 200 mg) using a 30-minute IV infusion on Day 1 of each 3-week treatment cycle for up to 35 cycles.

Study sites should make every effort to target infusion timing to be as close to 30 minutes as possible. However, given the variability of infusion pumps from site to site, a window between -5 minutes and +10 minutes is permitted (ie, infusion time is 30 minutes -5 min/+10 min).

SAR444245

SAR444245 formulation and route of administration as described in the master protocol.

- Dose regimen: 24 µg/kg (or reduced to [REDACTED] µg/kg or another lower dose level recommended by Study Board) administered as an IV infusion over 30 minutes every 3 weeks on Day 1 of each cycle (21 days per cycle) for up to 35 cycles.

Non-investigational medicinal products

Please refer to the master protocol.

After 4 cycles, in case of permanent SAR444245 discontinuation and continuation of pembrolizumab treatment as part of AE management, premedication for SAR444245 no longer needs to be administered.

Statistical considerations:

Please refer to the master protocol for description of common statistical considerations. Substudy-specific analyses are summarized below.

- **Analysis of primary endpoint:**

- The complete response rate (CRR) will be summarized for the efficacy population with descriptive statistics. In addition, two-sided 90% CIs for CRR will be computed using the Clopper-Pearson method.

- **Analysis of secondary efficacy endpoints:**

[figure not shown]
- The objective response rate (ORR) will be summarized for the efficacy population with descriptive statistics. In addition, two-sided 90% CIs for ORR will be computed using the Clopper-Pearson method.

Data Monitoring/Other Committee: Yes

1.2 SCHEMA

1.2.1 Study design for Cohort A

Figure 2 - Graphical study design-Cohort A

C=Study cycle (1 cycle = 21 days); D=Study day; EOT=end of treatment; IMP=Investigational medicinal product; FDG-PET=fluorodeoxyglucose-positron emission tomography.

1.3 SCHEDULE OF ACTIVITIES (SOA)

Evaluation ^a	Screening	Treatment Period ^b								End of treatment	Observation period ^c			Survival phone call follow-up period ^d	Notes
		Cycle 1				Cycle 2-8		Cycle 9 – 35	EOT visit		Follow-up visit 1	Follow-up visit 2	Follow-up visit 3 and beyond		
Cycle day	D-28 to D-1	D1	D2 ^e	D3 ^e	D8	D14/ D15 ^f	D1(±3 days)	D8	D1(±3 days)	30 (±7) days after last IMP admin or prior to initiation of further therapy	3 months (±7 days) after last IMP admin	6 months (±7 days) after last IMP admin	Every 3 months ±7 days	Every 3 months ± 14 days	
Informed consent	X														
Inclusion/ Exclusion criteria	X														
IRT contact	X	X					X		X	X					
Demography, medical/surgical and disease history	X														See Section 8 in the master protocol
Performance status (ECOG or Lansky Scale)	X	X					X	X	X	X					See Appendix 13 in the master protocol
Body weight/Height ^g	X	X					X		X						

Evaluation ^a	Screening	Treatment Period ^b								End of treatment	Observation period ^c			Survival phone call follow-up period ^d	Notes
		Cycle 1				Cycle 2-8		Cycle 9 – 35	EOT visit		Follow-up visit 1	Follow-up visit 2	Follow-up visit 3 and beyond		
Cycle day	D-28 to D-1	D1	D2 ^e	D3 ^e	D8	D14/ D15 ^f	D1(±3 days)	D8	D1(±3 days)	30 (±7) days after last IMP admin or prior to initiation of further therapy	3 months (±7 days) after last IMP admin	6 months (±7 days) after last IMP admin	Every 3 months ±7 days	Every 3 months ± 14 days	
Full physical examination	X									X					
Directed physical examination		X			X	X	X		X		X				See Section 8.2.1 in the master protocol
Vital signs ^h	X	X	X	X	X	X	X	X	X	X					See Section 8.2.2 in the master protocol
SpO ₂ ^h	X	As clinically indicated													
Bone marrow biopsy		As clinically indicated to confirm complete response													See Section 8.1 in the master protocol

Evaluation ^a	Screening	Treatment Period ^b							End of treatment	Observation period ^c			Survival phone call follow-up period ^d	Notes
		Cycle 1			Cycle 2-8		Cycle 9 – 35	EOT visit		Follow-up visit 1	Follow-up visit 2	Follow-up visit 3 and beyond		
Cycle day	D-28 to D-1	D1	D2 ^e	D3 ^e	D8	D14/ D15 ^f	D1(\pm 3 days)	D8	D1(\pm 3 days)	30 (\pm 7) days after last IMP admin or prior to initiation of further therapy	3 months (\pm 7 days) after last IMP admin	6 months (\pm 7 days) after last IMP admin	Every 3 months \pm 7 days	Every 3 months \pm 14 days
Spleen measurement	X	As clinically indicated to evaluate response												See Section 8.1 in the master protocol
12-Lead ECG	X	As clinically indicated												See Section 8.2.3 in the master protocol
LVEF	X	As clinically indicated												See Section 8.2.3 in the master protocol
Troponin	X	As clinically indicated			X (Cycle 4 Day 1)		As clinically indicated							See Section 8.2.3 and Section 10.2 in the master protocol

Evaluation ^a	Screening	Treatment Period ^b								End of treatment	Observation period ^c			Survival phone call follow-up period ^d	Notes
		Cycle 1				Cycle 2-8		Cycle 9 – 35	EOT visit		Follow-up visit 1	Follow-up visit 2	Follow-up visit 3 and beyond		
Cycle day	D-28 to D-1	D1	D2 ^e	D3 ^e	D8	D14/ D15 ^f	D1(±3 days)	D8	D1(±3 days)	30 (±7) days after last IMP admin or prior to initiation of further therapy	3 months (±7 days) after last IMP admin	6 months (±7 days) after last IMP admin	Every 3 months ±7 days	Every 3 months ± 14 days	
Pregnancy test	X	X					X		X	X	X	X			See Section 8.2.5 and Section 10.2 in the master protocol
Blood chemistry ^h	X	X	X	X	X	X	X		X	X	X				See Section 10.2 in the master protocol
Tumor Lysis Laboratory Tests ⁱ		X	X	X											
Hematology ^h	X	X	X	X	X	X	X		X	X	X				
T3, FT4, TSH and cortisol ^j	X						X		X	X	X				See Section 10.2 in the master protocol

Evaluation ^a	Screening	Treatment Period ^b							End of treatment	Observation period ^c			Survival phone call follow-up period ^d	Notes
		Cycle 1			Cycle 2-8		Cycle 9 – 35	EOT visit		Follow-up visit 1	Follow-up visit 2	Follow-up visit 3 and beyond		
Cycle day	D-28 to D-1	D1	D2 ^e	D3 ^e	D8	D14/ D15 ^f	D1(\pm 3 days)	D8	D1(\pm 3 days)	30 (\pm 7) days after last IMP admin or prior to initiation of further therapy	3 months (\pm 7 days) after last IMP admin	6 months (\pm 7 days) after last IMP admin	Every 3 months \pm 7 days	Every 3 months \pm 14 days
Coagulation ^k	X	As clinically indicated							X					See Section 10.2 in the master protocol
Urinalysis ^l	X	On C1D1 and C2D1, then as clinically indicated							X					See Section 10.2 in the master protocol
Hepatitis serology, CD4+ counts and viral load	X ^m	As clinically indicated												See Section 10.2 in the master protocol
IMP		X					X		X					
Hospitalization ^o		X	X	X										

Evaluation ^a	Screening	Treatment Period ^b								End of treatment	Observation period ^c			Survival phone call follow-up period ^d	Notes
		Cycle 1				Cycle 2-8		Cycle 9 – 35	EOT visit		Follow-up visit 1	Follow-up visit 2	Follow-up visit 3 and beyond		
Cycle day	D-28 to D-1	D1	D2 ^e	D3 ^e	D8	D14/ D15 ^f	D1(±3 days)	D8	D1(±3 days)	30 (±7) days after last IMP admin or prior to initiation of further therapy	3 months (±7 days) after last IMP admin	6 months (±7 days) after last IMP admin	Every 3 months ±7 days	Every 3 months ± 14 days	
AE/SAE assessment ^p	X	Continuous throughout treatment period								X					See Section 8.3 in the master protocol
Prior/Concomitant Meds	X ⁿ	Continuous throughout treatment period													See Section 6.8 in the master protocol
First subsequent anti-cancer therapy										X	X	X	X		
Survival status														X	
Pharmacokinetic (PK) / Pharmacodynamic (PD) / Immunogenicity assessments															
PK	See PK Flow-Charts in Section 1.5														
ADA															

Evaluation ^a	Screening	Treatment Period ^b							End of treatment	Observation period ^c			Survival phone call follow-up period ^d	Notes
		Cycle 1			Cycle 2-8		Cycle 9 – 35	EOT visit		Follow-up visit 1	Follow-up visit 2	Follow-up visit 3 and beyond		
Cycle day	D-28 to D-1	D1	D2 ^e	D3 ^e	D8	D14/ D15 ^f	D1(\pm 3 days)	D8	D1(\pm 3 days)	30 (\pm 7) days after last IMP admin or prior to initiation of further therapy	3 months (\pm 7 days) after last IMP admin	6 months (\pm 7 days) after last IMP admin	Every 3 months \pm 7 days	Every 3 months \pm 14 days
PDy - Blood and tumor tissue collection ^f	See Biomarker Flow-Chart in Section 1.4													
Tumor assessment														
CT/MRI ^g	X						X		X	X	X	X	X	See Section 8.1.1 in the master protocol
Brain imaging ^h	If clinically indicated													See Section 8.1.1 in the master protocol
FDG-PET ^g	X	As clinically indicated, and must be performed for the 9-week and 18-week on-treatment assessments												See Section 8.1.1 in the master protocol

- a Evaluation: Screening assessments to be performed prior to first IMP administration unless otherwise indicated. Baseline evaluations should be completed within 7 days prior to the first dose of IMP, except for tumor assessment that may be performed within 28 days prior to IMP administration, and unless specified otherwise. There is no need to perform Cycle 1 Day 1 laboratory assessments that have been performed as part of screening within 3 days prior to first IMP administration. During the study treatment period, all assessments must be performed, and results should be reviewed by the investigator **prior to IMP administration** at that visit. After Cycle 1, samples for laboratory assessments (excluding PK & biomarker) can be collected up to 3 days prior to IMP administration. ICF must be signed before any study-specific procedures are performed and can be signed more than 28 days prior to first IMP administration. Screening time indicates the maximum time frame relative to the first IMP administration in which study procedures used to support eligibility are done.
- b Cycle: A treatment cycle is 21 days. See details in [Section 6.1](#) for IMP administration. If treatment cycles are adjusted, all procedures except tumor assessment imaging will be completed according to the Cycle number. Tumor assessment imaging will be performed at fixed time points from C1D1 regardless of any treatment delays.
- c Observation Period: Participants who enter the Observation period will be followed differently depending on the reason leading to permanent study treatment discontinuation. See Section 4.1 of the master protocol. For participant's convenience, all Follow-up assessments may occur during the same visit as that when tumor assessment is performed.
- d Survival Phone Call Follow-Up Period: Once the participant stops the tumor assessments due to PD or starts a new antineoplastic therapy, the participant moves into the Survival Follow-up Period and should be contacted by telephone approximately every 3 months \pm 14 days to assess for survival status. Updated survival status may be requested by the Sponsor at any time during the study.
- e Visits on C1D2, D3 are for safety-run in participants only.
- f Study Board may decide to cancel safety assessment on C1D15, upon agreement with Sponsor, if safety data justify it.
- g Weight/Height: Height is required at baseline only for patients > or =18 years old. For trial participants <18 years old, height should be assessed on day 1 \pm 1 of each cycle. Weight is required at Screening and prior to starting each infusion. The total dose will be calculated based on the weight on the day of the infusion or the most recent weight assuming it was assessed in a reasonable time frame according to Investigator assessment. Study sites should make every effort to measure body weight as close to the infusion day as possible considering the variability of local process from site to site. If the infusion is prepared with the most recent weight assessed in a reasonable time frame, this will not prevent to assess the weight on D1 of each cycle.
- h Blood chemistry/ hematology will be performed weekly on D1 pre-dose, D8 and D15 during Cycle 1, then on Day 1 of every cycle up to Cycle 12, then every other cycle during Treatment Phase. Visits and assessments on C1D2-D3 are only for participants in the safety run-in or participants who are hospitalized because of high tumor burden or at investigator's discretion. For these participants, vital signs, SpO₂ and complete blood counts (CBC) and differentials, chemistries (blood urea nitrogen (BUN), creatinine (Cr), alanine transaminase (ALT), aspartate transaminase (AST), alkaline phosphatase (Alk Phos), total bilirubin (TBil) will be obtained daily.
- i Tumor lysis laboratory tests (corrected calcium, magnesium, phosphate, uric acid, and lactate dehydrogenase [LDH] levels) will be obtained every 8 hours on C1D1 for safety run-in participants or participants who are hospitalized, and C1D2-D3 for safety run in or participants who are hospitalized because of high tumor burden or at investigator's discretion.
- j Endocrine function tests will be performed every 2 cycles throughout the entire treatment period and at EOT. During the Observation Period, they will be performed at Follow-Up Visit 1. They can also be performed as clinically indicated.
- k Coagulation includes international normalized ratio (INR), prothrombin time (PT) and activated partial thromboplastin time (aPTT).
- l Urinalysis will be performed on C1D1 and C2D1, then as clinically indicated during the treatment period, and will be performed at Follow-Up Visit 1.
- m For participants with known HIV, hepatitis B and hepatitis C infection under antiviral treatment to confirm controlled infection, and for all participants in France (see details and specific instructions in Section 10.2 and Section 10.7 in the master protocol, and [Section 10.7](#) in this substudy 01).
- n Prior medications that are received within 30 days before the first dose of IMP.
- o Hospitalization for 48 h for safety run-in participants or for participants with a high tumor burden or at investigator's discretion.
- p AE/SAE assessment: Severity will be graded according to NCI-CTCAE v 5. ICANS and CRS will be graded using ASTCT criteria integrated with central laboratory cytokine results ([2](#)).
- q The initial tumor imaging FDG-PET CT and/or MRI will be performed within 28 days prior to C1D1. Scans performed as part of routine clinical management are acceptable for use as the screening scan if they are of diagnostic quality and performed within 28 days prior to the date of enrollment. On study imaging will be performed every 9 weeks (63 \pm 7 days) after the date of first IMP and if clinically indicated. FDG-PET must be performed for the 9-week and 18-week on-treatment assessments. Imaging studies should follow calendar days and should not be adjusted for delays in cycle starts or extension. The same imaging technique should be used in a participant throughout the trial. After Week 45 tumor imaging should be performed every 12 weeks (84 \pm 7 days). CT scan of the chest, abdomen, pelvis and any other locations with suspicion or evidence of disease involvement is required for the baseline and follow-up assessments.
- r If a tumor biopsy was obtained from a target lesion during eligibility assessment, it is preferred to obtain a new baseline scan. Tumor biopsy should be considered for new lesions if their pathologic etiology is ambiguous.
- s Brain CT/MRI: To be performed if clinically indicated.

Amended Clinical Trial Protocol 01 (Substudy 01)
SAR444245-ACT16941

[figure not shown]
28-Apr-2022
Version number: 1

Abbreviations: ADA = Anti-drug antibodies; AE = Adverse event; ASTCT = American Society for Transplantation and Cellular Therapy; C = Cycle; CT = Computed tomography; D = Day; ECG = Electrocardiogram; ECOG = Eastern Cooperative Oncology Group; EOT = End-of-treatment; FDG-PET = fluorodeoxyglucose-positron emission tomography; FT4 = Free thyroxine; FU = Follow-up visit; HBsAg = Hepatitis B surface antigen; HCV = Hepatitis C virus; HIV = Human immunodeficiency virus; ICANS = Immune effector cell-associated neurotoxicity syndrome; ICF = Informed consent form; IMP = Investigational medicinal product; LVEF = Left ventricular ejection fraction; MRI = Magnetic resonance imaging; NCI-CTCAE = National Cancer Institute Common Terminology Criteria for Adverse Events; PD = Progressive disease; PDy = Pharmacodynamic; PK = Pharmacokinetic; Q3W = Every 3 weeks; SAE = Serious adverse event; TSH = Thyroid stimulating hormone.

Amended Clinical Trial Protocol 01 (Substudy 01)
SAR444245-ACT16941

28-Apr-2022
Version number: 1

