- a Blood Chemistry/hematology should be done with an overnight fasting if possible (should not interfere with hydration requirements). It will be performed weekly on D1 pre-dose, D8 and D15 (D15 for participants who receive Q3W only) during Cycle 1, then on Day 1 of every cycle up to Cycle 12, then every other cycle during Treatment Phase. Visits and assessments on C1D2-D3 will be performed for participants in the safety run-in or participants who are hospitalized because of high tumor burden or at Investigator's discretion. During the Observation Period, it will be performed at Follow-Up Visit 1. It can also be performed as clinically indicated. In case of Grade ≥ 3 liver function abnormal tests, additional tests will be repeated every 2-3 days until recovery to baseline value.
- b Modification of Diet in Renal Disease (MDRD) equation: Glomerular filtration rate (mL/min/1.73 m²) = 175 × (Serum Creatinine)-1.154 × (Age)-0.203 × (0.742 if Female) × (1.212 if African American)
- c Bicarbonate or carbon dioxide (venous) (if bicarbonate or carbon dioxide are assessed only on arterial blood at site level, to be done only if clinically indicated)
- d Endocrine function tests will be performed every 2 cycles throughout the entire treatment period and at EOT. During the Observation Period, they will be performed at Follow-Up Visit 1. They can also be performed as clinically indicated.
- e Pregnancy Test: Women of childbearing potential must have a negative urine pregnancy test result within 72 hours prior to first IMP administration of each cycle, at EOT and every 30 (± 7) days until 120 days (or refer to the individual substudy protocol) after the last dose of study treatment. If urine pregnancy results cannot be confirmed as negative, a serum pregnancy test will be required. Pregnancy tests (serum and/or urine tests) should be repeated if required by local guidelines.

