10.12 APPENDIX 12 GUIDELINES FOR THE MANAGEMENT OF TUMOR LYSIS SYNDROME (TLS)

TLS is a metabolic derangement that is the result of rapid destruction of tumor cells. TLS is common in hematological malignancies and can cause several side effects; some of them may become life-threatening. Early recognition of TLS and initiation of therapy is essential.

Intravenous hydration is recommended for all participants prior to start of SAR444245 infusions and is left to Investigator judgment for further cycles.

The participants at greatest risk of TLS are those with a high tumor burden prior to treatment. These patients should be monitored closely, and appropriate precautions should be taken (such as use of prophylactic uric acid lowering agents (eg, allopurinol or rasburicase) and regular measurement of electrolytes.

This appendix provides parameters to be checked in case of TLS suspicion and recommendations for TLS management. Abnormalities listed in this appendix do not exclusively support TLS diagnosis and any differential diagnosis also needs to be assessed, if appropriate.

TLS may present with laboratory parameters changes, clinical manifestations, or both as indicated in [Table 13](#).

Table 13 - Tumor lysis syndrome definitions**Table I. Cairo-Bishop definition of laboratory tumour lysis syndrome.**

Uric acid	$x \geq 476 \text{ } \mu\text{mol/l}$ or 25% increase from baseline
Potassium	$x \geq 6.0 \text{ mmol/l}$ or 25% increase from baseline
Phosphorous	$x \geq 2.1 \text{ mmol/l}$ (children), $x \geq 1.45 \text{ mmol/l}$ (adults) or 25% increase from baseline
Calcium	$x \leq 1.75 \text{ mmol/l}$ or 25% decrease from baseline

Modified from Hande and Garrow (1993).

Laboratory tumour lysis syndrome (LTLS) is defined as either a 25% change or level above or below normal, as defined above, for any two or more serum values of uric acid, potassium, phosphate, and calcium within 3 d before or 7 d after the initiation of chemotherapy. This assessment assumes that a patient has or will receive adequate hydration (\pm alkalinization) and a hypouricaemic agent(s).

Table II. Cairo-Bishop definition of clinical tumour lysis syndrome.

- (1) Creatinine*: $x \geq 1.5 \text{ ULN}^\dagger$ (age >12 years or age adjusted)
- (2) Cardiac arrhythmia/sudden death*
- (3) Seizure*

Modified from Hande and Garrow (1993).

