Clinical tumour lysis syndrome (CTLS) assumes the laboratory evidence of metabolic changes and significant clinical toxicity that requires clinical intervention. CTLS is defined as the presence of LTLS and any one or more of the above-mentioned criteria.

*Not directly or probably attributable to a therapeutic agent (e.g. rise in creatinine after amphotericin administration).

† Creatinine levels: patients will be considered to have elevated creatinine if their serum creatinine is 1.5 times greater than the institutional upper limit of normal (ULN) below age/gender defined ULN. If not specified by an institution, age/sex ULN creatinine may be defined as: $> 1 < 12$ years, both male and female, $61.6 \text{ } \mu\text{mol/l}$; $\geq 12 < 16$ years, both male and female, $88 \text{ } \mu\text{mol/l}$; ≥ 16 years, female, $105.6 \text{ } \mu\text{mol/l}$; ≥ 16 years, male, $114.4 \text{ } \mu\text{mol/l}$.

For participants in the safety run-in or participants who are hospitalized because of high tumor burden or at Investigator's discretion, tumor lysis laboratory tests (corrected calcium, magnesium, phosphate, uric acid, and lactate dehydrogenase [LDH] levels) will be obtained per details provided in the individual substudy).

Cardiac monitoring and admission to the ICU is required if TLS is established, as well as continuing laboratory monitoring every 4-6 hours. Additional measures to treat metabolic derangements associated with TLS may be required, as shown in [Table 14](#).

Prophylaxis against TLS may be required depending on the patient's risk for TLS, as described below.

Low-risk is defined as:

- Patients with low tumor burden (WBC $\leq 50 \times 10^9/l$ and normal LDH level)
- Patients receiving low intensity cytoreductive therapy
- Normal pre-existing uric acid
- Adequate hydration
- No tumor infiltration in the kidney

High-risk is defined as:

- Hematological malignancies with high proliferative rate
- High tumor burden (WBC $\geq 50 \times 10^9/l$ and high LDH level)
- Elevated uric acid level
- Patients receiving intensive cytoreductive therapy
- Poor hydration
- Leukemia infiltration of the kidney

Recommendations for **intravenous hydration** during SAR444245 treatment in patients at high risk for TLS, include the following:

- [REDACTED]
- [REDACTED]
- [REDACTED]
- [REDACTED]

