Tumor lysis laboratory tests (corrected calcium, magnesium, phosphate, uric acid, and lactate dehydrogenase [LDH] levels) will be obtained every 8 hours on C1D1 for safety run-in participants and participants who are hospitalized, and C1D2-D3 for safety run in or participants who are hospitalized because of high tumor burden or at investigator's discretion (refer to [Section 1.3 SOA](#) for details). If it occurs, appropriate treatment will be initiated that will include correction of serum calcium, potassium, or phosphorus abnormalities, and treatment of hyperuricemia with allopurinol and/or rasburicase, as indicated in Appendix 12 of the master protocol ([30](#)).

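### Footnote e of both substudy Schedules of Activities limits Cycle 1 Day 2 and 3 visits to the safety run-in, against the wider rule stated everywhere else

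*Protocol*

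**What the plan says.** Section 1.3 of each substudy attaches footnote e to the Cycle 1 Day 2 and Day 3 column headings. It reads the same in both: "Visits on C1D2, D3 are for safety-run in participants only".

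Footnote h of the same tables says: "Visits and assessments on C1D2-D3 are only for participants in the safety run-in or participants who are hospitalized because of high tumor burden", and then adds the investigator's discretion. Footnote o covers the inpatient stay: "Hospitalization for 48 h for safety run-in participants or for participants with a high tumor burden", again with discretion added. Footnote i sets eight-hourly tumor-lysis tests on Days 2 and 3 for the same wider group. The tumor lysis sections (6.5.4.7 in Substudy 01, 6.5.4.6 in Substudy 03) repeat this: "C1D2-D3 for safety run in or participants who are hospitalized because of high tumor burden".

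In the master protocol, note a to Table 6 (Appendix 2) says: "Visits and assessments on C1D2-D3 will be performed for participants in the safety run-in or participants who are hospitalized because of high tumor burden". Appendix 12 introduces the lysis tests with "For participants in the safety run-in or participants who are hospitalized because of high tumor burden or at Investigator's discretion, tumor lysis laboratory tests" and sends the reader to the substudy for the details.

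**The concern.** Footnotes e and h each claim to be exclusive, and they name different groups. Splitting them into visits (e) and assessments (h) does not reconcile them, because h covers both.

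The participants on whom they disagree are those outside the run-in who are admitted for tumor burden or at the investigator's discretion. Appendix 12 says of the first of these: "The participants at greatest risk of TLS are those with a high tumor burden prior to treatment". A site that applied footnote e literally would skip their Day 2 and 3 lysis panels, vital signs, oxygen saturation, blood counts and chemistry. Section 8 of the master protocol makes adherence to the Schedule of Activities mandatory and allows no waivers, so whichever footnote a site follows for such a participant, it departs from the other.

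**Working it through.** No sample size, power or error rate is involved. The check is a count of every statement about who is seen, tested or admitted on these days, followed by a bound on the number affected.

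**Statements using the wider group**

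| Place | Subject | Count |
|---|---|---|
| Footnote h, both substudies | visits and assessments | 2 |
| Footnote i, both substudies | lysis tests | 2 |
| Footnote o, both substudies | 48-hour admission | 2 |
| Tumor lysis sections 6.5.4.7 and 6.5.4.6 | lysis tests | 2 |
| Master Table 6, note a | visits and assessments | 1 |
| Master Appendix 12 | lysis tests, timing left to the substudy | 1 |

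Total: 2 + 2 + 2 + 2 + 1 + 1 = 10. Nine of these are tied to Days 2 and 3, footnote o through its table row, which is marked on Days 1 to 3. Appendix 12 is the exception.

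**Statements using the narrower group:** footnote e, once in each substudy, so 2.

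**Outside the count.** Note c to the pharmacokinetic flowchart in each substudy places the Day 2 and Day 3 samples in the run-in and in hospitalized participants. The Substudy 01 change table, taken as context only, records footnote e as a clarification and gives no reason for narrowing the group.

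**Procedures marked on Days 2 and 3.** These are vital signs, chemistry and hematology (footnote h), lysis tests (footnote i) and hospitalization (footnote o). Each row footnote names the wider group, so no procedure on these days depends on footnote e alone.

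**Number of participants.** Each cohort plans 25 participants at the confirmed dose, with 6 to 10 of them in the run-in:

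- Outside the run-in: 25 − 10 = 15, or 25 − 6 = 19. These are ceilings, since only admitted participants are concerned.
- The documents do not give the share admitted. Assuming 10% to 40%: 0.10 × 15 = 1.5 and 0.40 × 19 = 7.6, so about 2 to 8 per cohort.

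**Tests per participant.** Eight-hourly sampling gives 24 / 8 = 3 lysis panels a day. That is 3 if the stay ends with Day 2 and at most 2 × 3 = 6. Six is a ceiling, because a 48-hour stay from Day 1 ends by Day 3. The daily safety set (vital signs, oxygen saturation, blood counts, chemistry) is due at most twice.

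**The case against.** The best reply is that the table corrects itself. Every procedure marked on Day 2 or 3 carries a row footnote with the wider rule, so a site would omit monitoring only by reading the column footnote and ignoring the row footnote on the same cell. This stands, and it is the main reason for the low rating. It does not make footnote e correct.

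Other safeguards also count:

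- Appendix 12 asks for close monitoring and regular electrolytes in high-burden patients, whatever the visit footnotes say.
- Table 6 note a allows chemistry and hematology when clinically indicated.
- Section 8.2.2 lets the investigator order inpatient vital signs to 24 hours outside the run-in.
- Appendix 12's referral to the substudy leads most naturally to footnote i and the tumor lysis section, both of which give the wider rule.

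The tally of ten can fairly be called generous. Four of the statements appear in both substudies, so the distinct count is six against one. Only three of the ten (footnote h twice, and Table 6 note a) speak of visits. The direction of the fix rests mainly on those three. The others agree with them, and none supports footnote e.

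The assumed share of 10% to 40% has no anchor in the documents. It also counts people to whom the conflicting rules apply, not people likely to miss a test.

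**Conclusion.** The inconsistency is real, and footnote e is the statement that is wrong. It is minor and worth correcting at the next amendment.

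The only firm size is the ceiling of 15 to 19 of 25 per cohort outside the run-in. The figure of about 2 to 8 rests on the assumed share admitted. The number who would actually miss a test should be smaller still, given the row footnotes.

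What could be lost is safety monitoring on Days 2 and 3. Day 1 lysis tests are unaffected. Run-in participants attend under either reading, so dose-limiting toxicity evaluation does not change, and neither does any efficacy endpoint. The Day 2 and 3 pharmacokinetic samples are governed by their own note.

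**What to change.** In Section 1.3 of both substudies, reword footnote e along these lines: *C1D2 and C1D3 visits apply to safety run-in participants, and to any other participant hospitalized because of high tumor burden or at the investigator's discretion.* This brings it into line with footnote h.

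The cost is one footnote in each of two documents. It adds no visit, test or admission beyond those that footnotes h, i and o already require, and it changes nothing in the SAP.
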